2. OBJECTIVES AND ENDPOINTS

Objectives	Endpoints
Primary objectives	Primary endpoints
To evaluate the efficacy of CS1001 in subjects with R/R ENKTL;	Objective response rate (ORR) assessed by IRRC according to Lugano 2014 classification
Secondary objectives	Secondary endpoints
To evaluate the efficacy of CS1001 in subjects with R/R ENKTL;	ORR assessed by investigators; CRR, PRR, TTR, DoR assessed by IRRC and investigators;
To evaluate the safety of CS1001 in subjects with R/R ENKTL	Severity and frequency of AEs, and frequency of SAEs
To evaluate the PK of CS1001	To determine the peak and trough serum concentration of CS1001
To evaluate the immunogenicity of CS1001	Number and percentage of subjects who develop ADA
Exploratory objectives	Exploratory endpoints
To evaluate the progression-free survival (PFS) and overall survival (OS) of R/R ENKTL subjects	6-months PFS rate, 6-month OS rate
To evaluate genetic aberrations in R/R ENKTL by whole-exome sequencing test of tumor tissues	The association between genetic aberrations and efficacy

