- Investigator causality attribution against the investigational product (yes or no)
- Investigator causality attribution against the investigational product
- Outcome

In addition, additional variables including intervention will be collected for SAEs.

It is important to distinguish between serious and severe AEs. Severity is to describe the intensity, while the definition of SAEs is listed in Section 7.2.1. An AE of severe intensity need not necessarily be considered serious. For example, nausea that persists for several hours may be considered severe nausea, but not an SAE. On the other hand, a stroke that results in only a limited degree of disability may be considered a mile stroke but would be an SAE.

Events will be assessed and graded based upon the NCI CTCAE v4.03. For events of uncoded CTCAE grade, mild, moderate, and severe events will be converted to CTCAE level as recommended by the NCI CTCAE guideline. The latest version of CTCAE can be downloaded from the web of cancer treatment and evaluation plan (http://ctep.cancer.gov).

Causality Assessment

The investigator will assess the causal relationship between the investigational product and each event, and answer 'definitely related', 'possibly related', 'unlikely related', 'definitely unrelated' and 'not evaluable' to the question 'Do you consider that there is a possibility that the event may have been caused by the investigational product?'

Refer to Section 7.3.1 for the causality assessment guideline.

Adverse Events Based on Signs and Symptoms

All AEs spontaneously reported by subjects or caregivers and AEs found through observation will be recorded in the eCRFs. The subject's symptoms and signs will be recorded in the Diagnosis record (if possible) during the collection of AEs. If the diagnosis is confirmed, however, with symptoms and signs that are unlikely to be caused by the diagnosis should be recorded separately.

Adverse Events Based on Laboratory Tests and Examinations

All results of the protocol mandatorily required laboratory tests, vital sign measurements, ECG and other safety assessments will be summarized in the Clinical Study Report (CSR). If a parameter is worsened than the baseline level and meets the SAE criteria, or it leads to subject withdrawal apart from disease progression (see Disease Progression), it will be reported as an AE.

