7.2 SERIOUS ADVERSE EVENTS

7.2.1 Definition of A Serious Adverse Event

According to the definition from ICH (International Council for Harmonisation), SAE is any adverse medical event that meets any of the following criteria:

- Results in death;
- Is life-threatening (Note: life-threatening in the context of an SAE refers to a reaction in which the patient was at risk of death at the time of the reaction; it does not refer to a reaction that hypothetically might have caused death if more severe);
- Requires in subject hospitalization or prolongation of existing hospitalization (except for hospitalization due to medical insurance reimbursement issue or hospitalization without approval by the study doctor);
- Results in persistent or significant disability/incapacity;
- Is a congenital anomaly/birth defect;
- Other medically significant events.

These medically significant events that may not result in death, be life-threatening or require hospitalization may be considered serious when they jeopardize the participant and may require intervention to prevent one of the outcomes listed above. Medical and scientific judgment should be exercised in deciding whether the event should be reported in the light of expedited reporting rules. Examples of medically significant events include allergic bronchospasm requiring intensive treatment in an emergency room or at home, blood dyscrasias or convulsions that do not result in subject hospitalization, or the development of drug dependency or drug abuse. For the avoidance of doubt, infection resulting from drug deterioration is considered as a medically significant event and should be reported according to the expedited reporting rules.

The following hospitalizations that occur during the course of study should not be considered as SAEs:

- Admission into an emergency room, outpatient, or other departments for <24 hours and not hospitalized (unless is considered "medically significant event" or life-threatening event);
- Planned optional operation before ICF signing;
- Protocol-specified admission for medical/surgical treatment or monitoring;
- Admission for physical assessment;
- Admission for a Grade 1 AE, including overnight hospitalization due to nonmedical reasons after investigational product administration;

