7.3.2 Assessment of Severity

For any AE, whether it is fatal or life-threatening, whether it leads to persistent or permanent disability, requires or prolongs hospitalization, or causes congenital anomaly will be recorded and graded based upon CTCAE v4.03. For an AE that is related to abnormal laboratory test finding(s), the event will be graded according to the clinical severity of the underlying condition; the grade is not necessarily in line with the grade of laboratory test finding.

Intensity will be graded based upon the following rules:

Grade	Description
-------	-------------

Grade 1	Mild; asymptomatic or mild symptoms; clinical or diagnostic observations only; or intervention not indicated	
Grade 2	Moderate; minimal, local, or non-invasive intervention indicated; or limiting age appropriate instrumental activities of daily living*	
Grade 3	Severe or medically significant, but not immediately life threatening; hospitalization or prolongation of hospitalization indicated; disabling; or limiting self care activities of daily living**	
Grade 4	Life-threatening consequences or urgent intervention indicated	
Grade 5	Death related to adverse event	

* Instrumental activities of daily living refer to preparing meals, shopping for groceries or clothes, using the telephone, financial management, etc.

** Examples of self-care activities of daily living include bathing, dressing, and undressing, taking food, using the toilet, and taking medications, as performed by patients who are not bedridden.

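### Section 7.2.1 excludes every admission for a Grade 1 adverse event from the SAE definition, so grade can override a grade-free hospitalization criterion and SAE frequency may be understated by an unknown amount

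*Protocol*

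**What the plan says.** Protocol Section 7.2.1 sets a one-criterion rule: "SAE is any adverse medical event that meets any of the following criteria". One criterion reads "Requires in subject hospitalization or prolongation of existing hospitalization". It carries exceptions for insurance reimbursement and for stays the study doctor did not approve, but none for grade.

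The same section then gives a list introduced by "The following hospitalizations that occur during the course of study should not be considered as SAEs". One item on it is "Admission for a Grade 1 AE, including overnight hospitalization due to nonmedical reasons after investigational product administration".

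Two other sections bear on this:

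- Section 7.1.3 asks investigators to keep serious and severe apart: "Severity is to describe the intensity, while the definition of SAEs is listed in Section 7.2.1". Its example of a mild but serious event is that "a stroke that results in only a limited degree of disability may be considered a mile stroke but would be an SAE" (mild is evidently meant).
- Section 7.3.2 defines Grade 1 as "Mild; asymptomatic or mild symptoms; clinical or diagnostic observations only; or intervention not indicated" and names an indicated hospital stay as a feature of Grade 3.

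Section 2 makes the safety endpoint "Severity and frequency of AEs, and frequency of SAEs", listed as secondary. The SAP, under Adverse Events, summarizes serious treatment-emergent events.

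**The concern.** Within one section, the hospitalization criterion ignores grade and the exclusion turns on it. If a Grade 1 event medically required admission, the criterion makes it an SAE and the exclusion removes it. An investigator following the text would leave it unflagged.

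Three things are at stake:

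- **The secondary endpoint.** The serious-event count loses the event.
- **Expedited reporting.** Section 7.2.2 requires SAEs to reach the sponsor or its CRO representative within 24 hours. An excluded event has no such deadline, and the additional variables that Section 7.1.3 collects for SAEs are not gathered.
- **Late events.** Table 7 stops collecting new adverse events once safety follow-up ends and keeps only drug-related SAEs and events already ongoing. A new drug-related Grade 1 event with admission, starting after that point, would not be collected.

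**Working it through.** The documents give no expected SAE rate and no expected number of Grade 1 admissions, so there is no figure of the plan to reproduce. The check is mainly a comparison of texts.

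**Step 1: how far the exclusion reaches.** The bullet names admission for a Grade 1 event and then adds the non-medical overnight stay with the word *including*. The stay is an example, not a limit. The first bullet in the list, on attendances under 24 hours, is overridden if the event is medically significant or life-threatening. The Grade 1 bullet has no such override.

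**Step 2: where the exclusion changes a classification.** Take a Grade 1 event with an admission that meets no other SAE criterion.

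| Was the admission required by the event? | Criterion alone | Criterion plus exclusion |
|---|---|---|
| No | Not an SAE | Not an SAE |
| Yes | SAE | Not an SAE |

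The grade clause has an effect only in the second row.

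**Step 3: can the second row be occupied?** Section 7.3.2 makes it uncommon, since a need for hospitalization points to Grade 3. Two parts of that section keep it from being empty by definition. Grade 1 includes events handled by clinical or diagnostic observation, which can take place in hospital. An event tied to a laboratory abnormality is graded by the clinical severity of the underlying condition, so its grade can be lower than that of the laboratory value. Appendix 13.4 describes immune-related presentations with few or no symptoms (lung infiltrates, raised liver tests, thyroid changes). None of this shows that such patients will be admitted; it shows only that the case is possible.

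**Step 4: direction.** The exclusion removes events and adds none. A subject drops out of the SAE proportion only if the event was graded 1, it truly required admission, it met no other SAE criterion, and the subject had no other SAE.

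**Step 5: scale only.** Inputs: N = 80 (approximate planned enrollment, Protocol Section 4) as denominator; k = number of affected subjects (assumed; not in the documents). Loss = 100 × k/80 percentage points. To show this against sampling error, assume 20 subjects are flagged under the present text, 20/80 = 25.0%, with exact Clopper-Pearson 95% intervals.

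| k (assumed) | Loss, points | Proportion with k added back | 95% CI |
|---|---|---|---|
| 0 | 0 | 20/80 = 25.0% | 16.0 to 35.9 |
| 1 | 1.25 | 21/80 = 26.25% | 17.0 to 37.3 |
| 2 | 2.5 | 22/80 = 27.5% | 18.1 to 38.6 |
| 4 | 5.0 | 24/80 = 30.0% | 20.3 to 41.3 |

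In each row the shift lies well inside the interval around 25.0%.

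**The case against.** The strongest reply is that the bullet mostly restates the criterion. On the protocol's own scale a Grade 1 event seldom requires admission, and one that did would normally be graded higher and fall outside the bullet. This stands as an argument that cases are few. It does not rescue the wording, because the clause does nothing except in the cases where admission was required.

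Several narrower points also stand:

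- Section 7.1.3 does not say outright that severity may never decide seriousness. It separates the two ideas and refers to Section 7.2.1 for the definition. Its stroke example concerns residual disability and does not mention admission, so the bullet is in tension with 7.1.3 and does not flatly contradict it.
- The list excludes hospitalizations. It does not switch off the other criteria (life-threatening, disability, medically significant), which still apply to a Grade 1 event.
- The event is not lost from the data during treatment and safety follow-up. Section 7.1.3 records all adverse events in that period, and Section 7.3.2 records for any event whether a hospital stay was needed or lengthened. Section 7.6 also sends qualifying liver findings to the sponsor within 24 hours whether or not they are serious.
- The late-event gap applies only to a new, drug-related Grade 1 event with admission that starts after safety follow-up, which is a remote case.
- SAE summaries are descriptive, and the SAP separately tabulates Grade 3 or higher, treatment-related and immune-related events and those leading to discontinuation or interruption. The primary endpoint is untouched.

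A reader might infer that SAE frequency *is* understated, or might put a range on the number of subjects affected. The documents support neither: they give no count of Grade 1 admissions, and zero is possible. The request in Section 1.2.3 for attention to early immune-related symptoms concerns timely dose modification and intervention; it does not say that mild cases will be admitted.

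**Conclusion.** The inconsistency is real and in force. Section 7.2.1 adopts a hospitalization criterion without a grade threshold and then lets Grade 1 cancel it, so following the text can misclassify a medically required admission. The effect runs one way: SAE frequency may be understated, never overstated, by this clause.

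The size cannot be estimated from the documents. It is probably small and may be nil. The 1.25 points per affected subject assumes 80 treated subjects and no other SAE in that subject; the values of k and the 25.0% base rate are illustrations. The point merits a wording correction and a data check. It does not call the efficacy analysis or the general recording of adverse events into question.

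**What to change.** Limit the Section 7.2.1 bullet to admissions not medically required by the event, and keep the non-medical overnight stay after dosing as the example. One possible wording: *admission that the adverse event did not medically require, such as an overnight stay after dosing for non-medical reasons*. Read the neighboring exclusion for physical assessment in the same way. Otherwise an admission to observe or work up a Grade 1 event could still be excluded by that route. This brings 7.2.1 into line with 7.1.3 and 7.3.2 without altering either.

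Before database lock, query Grade 1 events recorded as needing or lengthening a hospital stay and reclassify those that meet the criterion. The field should already exist, since Section 7.3.2 requires it for any adverse event. The query cannot recover new events after safety follow-up that were never collected; for those, only the corrected definition helps, and only from the time sites receive it.

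The cost is one line in an amendment or site letter, one data query, a few more SAE forms, and possibly a slightly higher reported SAE rate.

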7.2.2 Serious Adverse Event Reporting

Any SAE occurring from the time of ICF signing to 90 days after the last dose of investigational product or the start of new anti-cancer therapy, whichever occurs earlier, must be reported to the designated representative of CRO or the sponsor **no later than 24 hours** when it gets learned of, regardless of causality with the investigational product. After the safety follow-up period, only treatment-related SAEs need to be recorded and reported.

Once an SAE occurs, the investigator should:

• Immediately take appropriate treatment measures for the subject and report to the sponsor as described above, and to drug regulatory authorities, health administrative authorities, and the Ethics Committee according to the local requirements.

Complete the SAE module in the EDC system, after which an automated email will be sent to the designated sponsor representative. In case EDC is down, all applicable modules of the sponsor's SAE form will be completed by the investigator/site staff. The investigator must assess the relationship of each SAE to each specific component of study treatment, complete and sign the SAE Report Form, and submit the completed form within 24 hours to the sponsor pharmacovigilance representative. Follow-up information is submitted in a new SAE report form and marked as the follow-up information of a previously reported SAE.

Any SAE that is unresolved at the end of study or subject withdrawal must be followed up until any of the following condition occurs:

- Event resolves; or
- Event stabilizes; or
- Event returns to baseline level (if baseline level available); or
- The event can be attributable to factors related with a medication other than the investigational product or unrelated with the investigator's behavior, or further information is unable to be obtained (when the subject or medical staff refuses to provide more information or when there's evidence showing the subject is lost to follow-up despite every effort made).

7.3 ASSESSMENT OF ADVERSE EVENTS AND SERIOUS ADVERSE EVENTS

The investigator or study doctor is responsible for the causality and severity assessments of AEs and SAEs, and the final review and confirmation of the accuracy of data and assessments.

Any non-clinically significant laboratory finding is not recorded as an AE or SAE. Clinically significant (documented as 'Abnormal finding with clinical significance') laboratory findings (for example clinical laboratory, hematology, or urinalysis) and any other abnormal assessment result (for example ECG and vital signs) must be recorded as an AE or SAE. Events in compliance with the definition of AE or SAE must be recorded as an AE or SAE. If the laboratory finding is a component of a syndrome, the syndrome or diagnosis (for example anemia) instead of the laboratory finding (decreased hemoglobin) should be recorded.

7.3.1 Causality Assessment

The investigator should determine the relationship between the AE and the investigational product based on the following criteria:

- **Definitely related:** there is a rational temporal relationship of the occurrence of an AE including clinical laboratory finding to the administration of the investigational product. The investigational product can explain the AE more than any other reason (for example the underlying disease, environmental or toxic factors, or other treatment received by the subject); the reaction after discontinuation of investigational treatment is clinically reasonable.
- **Possibly related:** there is a rational temporal relationship of the occurrence of an AE including clinical laboratory finding to the administration of the investigational product. The investigational product can explain the AE with equal rationality with any other reason (for example the underlying disease, environmental or toxic factors, or other treatment received by the subject); information on post-discontinuation reaction is unavailable or unclear.
- Unlikely related: other reasons (for example the underlying disease, environmental or toxic factors, or other treatment received by the subject) explain the AE (including laboratory findings) more than the investigational product
- **Definitely unrelated:** there is no rational temporal relationship of the occurrence of an AE to the administration of the investigational product. The AE has other more remarkable reasons (for example the underlying disease, environmental or toxic factors, or other treatment received by the subject).
- Not determined: the above information is not available and with no complementary data, making causality not determined.

Definitely related, possibly related, and not determined events are counted as related adverse events when statistical analyses for adverse events are performed.

7.3.2 Assessment of Severity

For any AE, whether it is fatal or life-threatening, whether it leads to persistent or permanent disability, requires or prolongs hospitalization, or causes congenital anomaly will be recorded and graded based upon CTCAE v4.03. For an AE that is related to abnormal laboratory test finding(s), the event will be graded according to the clinical severity of the underlying condition; the grade is not necessarily in line with the grade of laboratory test finding.

Intensity will be graded based upon the following rules:

Grade	Description
-------	-------------

Grade 1	Mild; asymptomatic or mild symptoms; clinical or diagnostic observations only; or intervention not indicated	
Grade 2	Moderate; minimal, local, or non-invasive intervention indicated; or limiting age appropriate instrumental activities of daily living*	
Grade 3	Severe or medically significant, but not immediately life threatening; hospitalization or prolongation of hospitalization indicated; disabling; or limiting self care activities of daily living**	
Grade 4	Life-threatening consequences or urgent intervention indicated	
Grade 5	Death related to adverse event	

* Instrumental activities of daily living refer to preparing meals, shopping for groceries or clothes, using the telephone, financial management, etc.

** Examples of self-care activities of daily living include bathing, dressing, and undressing, taking food, using the toilet, and taking medications, as performed by patients who are not bedridden.

7.4 HANDLING OF ADVERSE EVENTS

All clinical events and clinically significant laboratory AEs will be handled based upon the guideline in CTCAE v4.03.

The investigator will record AEs resulting from the treatment, remind the sponsor medical monitor to pay attention, and take appropriate actions in consultation with the sponsor's medical monitor. Subjects with AEs must be followed up regularly if possible, regardless of the AEs' relationship with the treatment, until resolution of the symptoms, all the abnormal laboratory values return to normal or baseline values or are confirmed irreversible, or the observed changes can be properly explained.

For Grade 3 or 4 laboratory test finding with clinical significance, the test should be repeated to confirm the finding, if possible. Every effort should be made to have the subject revisit the site within 3 days of obtaining the initial test result for repeating the test and taking appropriate actions.

7.5 REPORTING OF SPECIAL SITUATIONS

7.5.1 Definition of a Special Situation

Reporting of special situations includes reporting of a medication error, drug abuse, misuse, overdose, and pregnancy (regardless of its relationship with any AE). Reports of adverse infant reaction post breast milk exposure and Reports of adverse drug effects associated with product complaints or tip-offs due to occupational exposure are also included.

The Pregnancy Report is used to report any pregnancy after maternal or paternal exposure.

Medication error refers to any unintended error in the prescription, dispensing, or administration of medications made by healthcare providers, subjects, or consumers.

Drug abuse is defined as persistent or occasional intended overuse of medication by a subject.

Misuse is defined as intended, improper use of medication that is not in line with the protocol or prescribing information.

Medication overdose is defined as: occasional or intended use/injection of the investigational product in a dose exceeding the prescribed one. Overdose is defined as: the subject has taken (accidentally or intentionally) a dose exceeding the dose prescribed in the protocol by 20%.

A product complaint is a complaint due to potential bias in the manufacturing, packaging, or distribution of medication.

